- Hospital Acquired pneumonia (HAP) following extubation- clinician diagnosis and commencement of antibiotics from randomisation up to ICU discharge.

Safety Outcome Measures

Reportable safety events are described in section 7 of the CoReCCT Master Protocol.

Adverse event rates, including device-related

Adverse event rates related to endotracheal tube intubation within 1 hour of intubation, or tube change if allocated to intervention arm:

- *Traumatic insertion, bleeding*
- *Injury to the throat or trachea*
- *Dental damage*
- *Failed intubation*
- *Aspiration during intubation*
- *Pneumothorax*
- *Obstruction or kinking of the endotracheal tube*
- *Cuff leak*
- *Unintentional extubation*

Adverse event rates related to endotracheal tube intubation after one hour of intubation, or tube change if allocated to intervention arm, up to ICU discharge:

- *Tracheal stenosis*
- *Vocal cord injury / paralysis / Arytenoid dislocation*
- *Hoarse voice / voice changes*
- *Sinusitis*
- *Laryngo-tracheal stenosis*
- *Tracheomalacia*
- *Obstructive fibrinous tracheal pseudo membrane*
- *Pressure injuries related to tube securing or pressure from tracheal tube*

- *Tracheo-oesophageal fistula*
- *C-spine and spinal cord injuries due to intubation*

Patient reported and health-economics outcomes:

- Costs associated with use of NHS & personal social services (PSS) resources arising during hospital stay and after hospital discharge; personal expenditures (out-of-pocket costs) incurred by patients after hospital discharge. (also see section Health Economic Evaluation).
- Health-related quality of life using a widely used and recommended preference-based quality of life instrument (EQ-5D-5L) collected at 2 and 6 months.

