2.8 Randomisation

2.8.1 Randomisation

A bespoke online randomisation system will be developed, by the WCTU programming team. The system will be based on a computerised algorithm using the minimisation method for randomising patients. The randomisation sequence will be created, stratified by hospital site, if the patient is intubated prior to randomisation and prior enrolment into the Awake Prone trial. Patients will be randomised, in a ratio of 1:1 to the advanced airways protection device or the standard of care endotracheal tube (with or without the basic subglottic suction/standard cuff). Randomisation can happen up to 24 hours after primary intubation. **If randomised to the intervention arm, this may necessitate a tube change. The tube change should occur within 24 hours of the patient initially being intubated.**

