4.1 Pre-Specified Complications

As per the CoReCCT Safety Reporting Flowchart, adverse events that 1) occur at sites between randomisation and hospital discharge and 2) are not present on the CoReCCT Exemption List, must be reviewed for their presence on the PROTECT Airways Pre-Specified Complications List as given below (Table 2)

The duration of mechanical ventilation from randomisation to liberation is the primary objective of this study. Therefore, any clinically relevant intubation and mechanical ventilation related event occurring from the time of randomisation until ICU discharge will be recorded as pre-defined trial outcomes (see as listed in Safety Outcomes Section 2.2 above and SAE reporting exemptions below).

Table 3 Pre-Specified Complications List (safety outcomes)

Pre-Specified Complications List (safety outcomes)

Adverse event rates related to endotracheal tube intubation within one hour of intubation or tube change if allocated to intervention arm:

- *Traumatic insertion, bleeding*
- *Injury to the throat or trachea*
- *Dental damage*
- *Failed intubation*
- *Aspiration during intubation*
- *Pneumothorax*
- *Obstruction or kinking of the endotracheal tube*
- *Cuff leak*

- *Unintentional extubation*

Adverse event rates related to endotracheal tube intubation after one hour of intubation, or tube change if allocated to intervention arm, up to ICU discharge

- *Tracheal stenosis*
- *Vocal cord injury / paralysis / arytenoid dislocation*
- *Hoarse voice / voice changes*
- *Sinusitis*
- *Laryngo-tracheal stenosis*
- *Tracheomalacia*
- *Obstructive fibrinous tracheal pseudo membrane*
- *Pressure injuries related to tube securing or pressure from tracheal tube.*
- *Tracheo-oesophageal fistula*

- *C-spine and spinal cord injuries due to intubation*

As per the CoReCCT Safety Reporting Flowchart, if the event is present on the Pre-Specified Complications List, the event must be recorded on the appropriate CRF as an outcome and does not need to be reported as an SAE. If the event is not on the list, it must be assessed for seriousness and the remainder of the flowchart should be followed to determine next steps.

The target population for the trial is the broad group of patients that require intubation and mechanical ventilation. These patients are the sickest in the hospital and are at risk of physiological deterioration, including the need for increased organ support, and death. These events are captured as clinical outcomes.

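### The first-hour safety list pre-defines no physiological event, although only device-arm patients already intubated at randomisation may have a trial-driven tube change, and its window differs between arms

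*Protocol*

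**What the plan says.** Section 2.3 sets up a group of safety outcomes headed "Adverse event rates related to endotracheal tube intubation within 1 hour of intubation, or tube change if allocated to intervention arm". It holds nine items: traumatic insertion or bleeding, throat or tracheal injury, dental damage, failed intubation, aspiration, pneumothorax, "Obstruction or kinking of the endotracheal tube", cuff leak and unintentional extubation. Table 3 in section 4.1 repeats the same nine.

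Section 2.8.1 explains where the tube change comes from. "Randomisation can happen up to 24 hours after primary intubation", and "If randomised to the intervention arm, this may necessitate a tube change". Prior intubation is a minimisation factor: the allocation is "stratified by hospital site, if the patient is intubated prior to randomisation and prior enrolment into the Awake Prone trial".

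Section 4.1 routes events as follows. It covers adverse events from randomisation to hospital discharge that "are not present on the CoReCCT Exemption List". An event on the Table 3 list is recorded as an outcome and requires no SAE report. For any other event the rule is: "If the event is not on the list, it must be assessed for seriousness and the remainder of the flowchart should be followed". The section also says that these patients are at risk of physiological deterioration, more organ support and death, and adds: "These events are captured as clinical outcomes". All-cause mortality is an outcome at ICU discharge, hospital discharge, 2 months and 6 months.

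**The concern.** For a patient already intubated, allocation to the device can mean exchanging a tube during ventilation. An already-intubated control has no such trial-driven step. The list heading itself treats the exchange as an exposure whose harms should be counted, but loss of oxygenation or circulation during it is not among the items.

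Section 4.1 also undertakes to record every clinically relevant intubation or ventilation event, from randomisation to ICU discharge, as a pre-defined outcome. It then points to lists that omit these events.

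At stake is the balance of benefit and harm. The sample size is built on a gain of one day of ventilation (6 days against 5). A reader asked to exchange a tube for that gain needs to know the acute physiological cost of the exchange, measured in the same way in both arms.

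**Working it through.** This is mainly a comparison of sections. The arithmetic only illustrates scale.

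**1. Content of the list.** None of the nine first-hour items is severe hypoxaemia, cardiovascular collapse or cardiac arrest. The list for events after one hour holds later injuries such as stenosis, voice change, sinusitis, fistula and pressure injury, and does not contain them either.

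**2. Who is exposed.** A trial-driven tube change needs two conditions: device allocation, and intubation before randomisation. Patients randomised before intubation have one intubation in either arm.

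**3. Where an off-list event goes.**
- It is first screened against the Exemption List, which is not shown.
- If it is not exempt, it is assessed for seriousness by staff who, by section 2.11, cannot be blinded.
- Otherwise it can appear only through organ support or mortality, for which this protocol gives no window around the exchange.

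**4. The time window.** Take randomisation as hour 0 and intubation as hour -a, with a between 0 and 24.
- *Already-intubated control:* the first hour runs from -a to -a + 1. If a is 1 or more, it ends at or before randomisation, when collection starts. If a is below 1, only 1 - a hours of it remain.
- *Already-intubated device patient who is exchanged:* a full hour after the exchange is observed.
- Pneumothorax, tube obstruction, cuff leak and unintentional extubation can occur without any exchange, and the later list does not repeat them. For these, most already-intubated controls have little or no matching observation time.
- If sites instead recorded events before randomisation, the control figure would describe the primary intubation, which allocation cannot affect.

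**5. Scale.** The document's one relevant figure is 1097 per arm (2194 in total). It reproduces: hazard ratio 1.2^0.901 = 1.1785; Freedman events = (1.960 + 1.282)² × (2.1785/0.1785)² ≈ 1565; 1565 / (1 - 0.256 - 0.03) = 1565 / 0.714 ≈ 2192. Neither the share already intubated nor the event rate is given, so both are assumed:

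| Assumed share already intubated | Exchanges if all are changed | Events at 1% | Events at 5% |
|---|---|---|---|
| 30% | 1097 × 0.3 = 329 | 3.3 | 16 |
| 50% | 1097 × 0.5 = 549 | 5.5 | 27 |
| 80% | 1097 × 0.8 = 878 | 8.8 | 44 |

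**6. Would a comparison be informative?** The check is a two-sided 5% test of two proportions by normal approximation within the already-intubated stratum, with n per arm = 1097 × share. Power = Φ{[|p2 - p1| - 1.96 √(2p̄(1 - p̄)/n)] / √([p1(1 - p1) + p2(1 - p2)]/n)}. The rates are again assumed.

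| Share (n per arm) | 1% v 3% | 3% v 6% | 5% v 10% |
|---|---|---|---|
| 25% (274) | 39% | 40% | 60% |
| 50% (549) | 66% | 67% | 88% |
| 75% (823) | 83% | 84% | 97% |

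A comparison would be useful if half or more are already intubated and the rates are not very low. Below that it would be descriptive.

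**The case against.** The strongest reply has five parts.

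*The exchange is already studied.* A reader might infer that the acute harm of the tube change is not compared at all. The protocol does not support that: the list heading covers the tube change, and failed intubation, aspiration, pneumothorax, obstruction, cuff leak and unintentional extubation are acute harms of it. Only the physiological part is missing. This stands.

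*The wider safety framework is elsewhere.* A reader might also infer that these events are never a planned comparison. That cannot be shown. Section 2.3 refers to the CoReCCT Master Protocol for reportable safety events and the core outcome set, and has a general line on adverse event rates. The point is therefore limited to this protocol.

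*Serious harm would still show.* Deaths and added organ support are captured, and the primary outcome runs from randomisation under a treatment-policy strategy, so an exchange that prolongs ventilation counts against the device. This is true, and it means net benefit is not beyond judgement. But a transient severe event, or a small number of arrests, would not be visible as such in these outcomes.

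*Listing the events could weaken safety reporting.* Under section 4.1 a listed event need not be reported as an SAE. Simply adding cardiac arrest to Table 3 would take it out of causality and expectedness assessment. This stands and shapes the fix.

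*The figures are assumed.* This also stands. Section 2.8.1 says only that a change may be needed, the pilot treats 80% adherence as green, some events could coincide with a listed item, and no background rate in controls is subtracted. A reader might take 3-44 as excess harm; it is not.

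**Conclusion.** The point holds in a limited form. This protocol pre-defines nine airway or tube-mechanical harms for the first hour and no physiological event, while a trial-driven tube change can fall only on device-arm patients already intubated at randomisation. Subject to the unseen master protocol, the acute physiological harm of that step rests on open-label SAE judgement and on outcomes with no window around the exchange. The first-hour windows are also unequal between arms among patients already intubated.

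The size cannot be derived from the document. The 329-878 exchanges and 3-44 events are gross upper illustrations under assumed shares of 30-80% and rates of 1-5%, with every such patient exchanged. The conclusion does not depend on them. It should be corrected in the protocol, because data not defined and collected prospectively cannot be reliably recovered by an analysis plan.

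**What to change.** - In section 2.3, pre-define severe hypoxaemia, cardiovascular collapse and cardiac arrest as safety outcomes, with definitions set by the investigators.
- Collect them in both arms over the same post-randomisation window, for example the first 24 hours. By the protocol's own timing, a patient intubated a hours before randomisation has any tube change by hour 24 - a, so this window contains every exchange made on schedule.
- Report them by arm and by intubation before randomisation, which is already a minimisation factor. Use the same clock for the listed items that can occur without an exchange.
- State that these events are recorded as outcomes in addition to SAE reporting, and that the Table 3 exemption from SAE reporting does not apply to them.
- If the master protocol already defines them, a cross-reference with the window and the by-arm report is enough.

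The cost is a few case report form fields and a short amendment. The ICU charts named in section 2.10 for source verification are one source, but hourly entries may miss brief desaturation or hypotension, so event notes should be used as well.

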2.4 Eligibility criteria

Patients are eligible to be included in the trial if they meet all the inclusion criteria and none of the exclusion criteria:

2.4.1 Inclusion criteria

1. Adult (age ≥ 18 years)
2. Need for invasive mechanical ventilation
3. Likely to remain ventilated for at least 24 hours post randomisation

2.4.2 Exclusion criteria

1. Intubated for more than 24 hours prior to randomisation
2. Treatment withdrawal anticipated within next 24 hours post randomisation
3. Presence of tracheostomy at screening

2.5 Participant identification / Screening

Staff will identify potential participants in appropriate clinical areas, such as emergency departments, critical care units, acute wards, operating theatres. Potential processes for identifying patients include referrals, screening in clinical areas, or review of electronic health systems using appropriate queries. We will work with each participating site to support the development of strategies to optimise screening in their hospital.

Screening information will be entered on to a trial web application, hosted by Warwick Clinical Trials Unit (WCTU). This will capture anonymised data on the numbers of patients meeting inclusion criteria for the trial but not entered into the trial along with the reasons for non-enrolment. These data are important to understand the generalisability of the recruited patient population.

Screening of patients will involve reviewing personal identifiable information. This may be undertaken by a member of the patient's existing clinical care team, or by a member of the hospital research team, depending on local arrangements. Screening and eligibility assessment may be undertaken by any individual clinically competent to undertake that role, as determined by the principal investigator. It is anticipated that this process may be undertaken at any time of day or night, provided appropriately trained staff members are available.

Patients who need intubating, or who have been intubated within the last 24 hours prior to randomisation are eligible for the trial. Confirmation that all eligibility criteria are met will be entered on to the trial web application prior to the patient being randomised.

2.6 Site Staff Training

Training for recruitment:

A programme of training will be provided to individuals at hospital sites with responsibility for the assessment of eligibility criteria and randomisation of participants. We will develop web-based training resources that enable site staff to complete training at a time convenient to them. If it is more convenient to specific individuals, training may be provided in person or via video conferencing. This training may be delivered by WCTU staff or by the site principal investigator, or a member of the site team that has been approved to deliver training by the principal investigator. Each hospital site will maintain a training completion log.

Training programme for delivering the intervention: To standardise the delivery of the intervention across and within sites, the Venner PneuX™ advanced airways protection device has a detailed manual and training programme[17]. The inclusion of this innovation will not change routine NHS practice, when handling patients who need assistance using a ventilator. Training will be provided to research, care teams and clinicians involved in delivery of usual airway clearance management, so that they are accustomed in delivering the intervention. Training videos, material and face-to-face training will be provided by the supplier (Qualitech Healthcare). The training programme consists of: (i) introduction to the Venner PneuX™ device (endotracheal tube and tracheal seal monitor); (ii) practical demonstration (subglottic irrigation and drainage); (iii) hands-on session; (iv) questions and answers; (iv) verification of understanding certificate; (v) training evaluation forms and training records. Online training resources will also be utilised : (i) PneuX System™ Tube Exchange [18] (ii) Irrigation with the PneuX System™ [19] (iii) Intubating with the PneuX System™ [20] Information on potential barriers during implementation and mitigating actions are detailed in online documentation [21].

Comparator

Standard care is to intubate a patient using a conventional endotracheal tube or endotracheal tube with basic subglottic suction and standard cuff (made of Polyvinyl Chloride (PVC)). These tubes have a single lumen subglottic port. Pressure within the cuff is checked every 12 hours (once per nursing shift). The subglottic port is aspirated every four hours to clear subglottic secretions, or more, if there is a high secretion load.

2.7 Informed consent

We have carefully considered the patient eligibility criteria. As described above, we made the trial eligibility criteria as broad and inclusive as possible. Ineligible groups are minimal and based on likely lack of efficacy (unlikely to be intubated longer than 24 hours), and tracheostomy formation, although there are tracheostomy versions of this system, here we view tracheostomy as a key outcome.

The trial will recruit from all hospital areas that treat patients with ventilation support likely to last 24 hours or more, and which can safely deliver the intervention. We will attempt to target patients as early as possible in their illness. This will increase the generalisability of our findings.

The consent process should be performed according to section 4.2.3 of the CoReCCT master protocol.

Once a patient who initially lacks mental capacity, regains capacity during their initial acute hospital admission or up to 30 days from randomisation, they will be informed about the trial and invited to consent to continue in the trial. There is no requirement to reaffirm consent in Scotland.

2.8 Randomisation

2.8.1 Randomisation

A bespoke online randomisation system will be developed, by the WCTU programming team. The system will be based on a computerised algorithm using the minimisation method for randomising patients. The randomisation sequence will be created, stratified by hospital site, if the patient is intubated prior to randomisation and prior enrolment into the Awake Prone trial. Patients will be randomised, in a ratio of 1:1 to the advanced airways protection device or the standard of care endotracheal tube (with or without the basic subglottic suction/standard cuff). Randomisation can happen up to 24 hours after primary intubation. **If randomised to the intervention arm, this may necessitate a tube change. The tube change should occur within 24 hours of the patient initially being intubated.**

2.8.2 Post-randomisation withdrawals, exclusions and moves out of region

Participants, or their consultee on their behalf, may request to be withdrawn from the trial at any time without prejudice. Withdrawing from the trial will not affect the participant or their care in any way.

Withdrawal should be handled as per section 6.8 of the CoReCCT master protocol.

In the event that a participant is transferred to another hospital, intervention delivery will usually stop at the point of transfer, unless the receiving institution is also a recruiting centre for PROTECT airways, if this is the case then the patient can continue in the trial. The recruiting hospital will liaise with the new hospital to facilitate collection of follow-up data.

Follow-up rates will be monitored by the Trial Management Group (TMG).

2.9 Trial treatments / intervention

- Intervention: A CE-marked advanced airways protection device (Venner PneuX™)
- Comparator: standard of care, conventional endotracheal tube (with or without basic subglottic suction and standard cuff).

Both the intervention and comparator group will receive standard care for mechanically ventilated patients, as directed by the clinical team. In line with the pragmatic nature of the trial, any escalation or de-escalation of standard treatment will be at the discretion of the clinical team, including oxygen therapy titration and use of non-invasive respiratory strategies. The treatment (comparator or intervention) will continue until:

- Successful unassisted breathing (no further requirement for mechanical ventilation)
- Trial intervention-related serious adverse event
- Death or discontinuation of active treatment

If the participant is extubated and then subsequently requires re-intubating:

1. If less than 48 hours from randomisation should be done using the intervention tube if allocated to the intervention arm.
2. If greater than 48 hours from randomisation should be done according to clinicians discretion.

Intervention

An advanced airways protection device consists of a flexible ETT with ports for subglottic suction/irrigation as well as a port to attach to an electronic system to maintain cuff pressure. The Venner PneuX™ device was recommended for testing in a large scale clinical trial by NICE in MTG48[5]. It is the only advanced airway system currently available in the NHS. Venner PneuX™ device is available in various sizes. We will test this system and the findings will be generalisable to future devices with similar design features and capabilities.

The Venner PneuX™ device is a flexible armoured ETT. It has a low-volume, low pressure cuff, that inflates uniformly without folds or creases. The key innovative design is the cuff which does not form microchannels and this prevents micro-aspiration during long term ventilation [18]. The endotracheal cuff and pilot balloon is connected to an electronic system that continuously maintains, monitors, and regulates the pre-set cuff pressure. It has three sub-glottic suction ports around the circumference to ensure that at least one port is patent for suctioning. Sub-glottic suction ports can facilitate irrigation and aspiration of secretions from the subglottic space.

Figure 2 Venner PneuX™ device - an advanced airways protection system

If there is an issue with the tube that requires a tube change then unless participant safety would be compromised participants in the intervention arm should be given another advanced airways protection device (Venner PneuX™).

